4.8 EVALUATION OF TRANSOPERATIVE BLEEDING

The intraoperative bleeding assessment will be quantitative, based on the blood collected in the collection bottle. The amount of distilled water used will be subtracted from the total aspirated volume. This value will be recorded at the time the suture is completed.

To assess bleeding from the second surgical site, the measurement will be taken at the time the suture is completed. The amount of distilled water used, along with the volume present in the collection bottle prior to the incision at the second site, will be subtracted. These values will be recorded, compared, and presented in the results.

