The removal of third molars is one of the most frequently performed procedures in dentistry, and can be carried out in a hospital setting under general anesthesia. In such cases, local anesthetics are often administered at the surgical site in addition to general anesthesia, to promote better hemostasis and postoperative analgesia. Bupivacaine is a local anesthetic commonly used in these situations. However, its known cardiotoxic and neurotoxic effects, as reported in the literature, have led to increased interest in safer alternatives, such as ropivacaine. **Objective:** to evaluate whether there is a significant difference between bupivacaine and ropivacaine in terms of postoperative analgesic efficacy, intraoperative hemostasis, and patient vital signs during the intraoperative period. **Materials and Methods:** This was a randomized, controlled, split-mouth clinical trial. The sample size was based on a similar previously published study and included 15 participants ($n = 30$). As this study also follows a split-mouth design, each of the 15 patients underwent two tooth extractions. All patients had indications for the removal of both lower third molars under general anesthesia. Surgical extractions were performed in a single session, with bupivacaine (Group A) administered at one surgical site and ropivacaine (Group B) at the other. The procedures were carried out at the Hospital de Clínicas de Porto Alegre. Vital signs were continuously monitored by the same anesthesiology team, with data collected at the time of drug injection (before and immediately after), as well as one minute and five minutes post-injection. Intraoperative bleeding was measured by calculating the volume of blood aspirated into the collection vial, from the time of incision to the final suture, at each surgical site. To minimize systemic interference from the anesthetic agents, their administration was alternated between patients. Postoperative analgesia was self-reported by the patients using a Visual Analog Scale (VAS) for each side at various postoperative time points. A descriptive analysis will be conducted on the clinical data obtained through these measurements.

Key-words: Third Molar; Anesthetics, Local; Surgery, Oral

SUMÁRIO

SUMMARY	5
1 INTRODUCTION	6
2 LITERATURE REVIEW	8
3 OBJECTIVES	10
4 METHODOLOGY	11
4.1 ETHINCAL ASPECTS	11
4.2 TYPE OF STUDY	11
4.3 LOCATION	12
4.4 SAMPLE	12
4.5 PREOPERATIVE CONDUCTS	13
4.6 SURGICAL TECHNIQUE	13

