3.2 SPECIFIC OBJECTIVES

- Measure the amount of intraoperative bleeding (in mL) during procedures performed with 0.5% bupivacaine with 0.2 mL of epinephrine and 0.75% ropivacaine with 0.2 mL of epinephrine.
- Assess potential changes in patients vital signs during and after the administration of local anesthetics.
- Compare the levels of postoperative discomfort associated with anesthetic agents using a visual analog scale (VAS).

JUSTIFICATION

Despite the well-known cardiotoxic and neurotoxic effects of bupivacaine, it continues to be widely used in oral and maxillofacial surgery. This study aims to compare and evaluate the feasibility of using a less toxic anesthetic agent in lower third molar removal surgeries under general anesthesia.

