4.6 SURGICAL TECHNIQUE

The procedure will be performed in a hospital setting, where patients undergo a single surgery for the extraction of the lower right and lower left third molars. Throughout the perioperative period, patients will be closely monitored, with their vital signs observed by both the surgical team and anesthesiology teams. As prophylaxis, patients will receive 900mg of clindamycin intravenously at the start of the procedure. The patient will be positioned supine on a hospital stretcher and placed under general anesthesia. Extra and intraoral antisepsis will be performed using a 0.12% chlorhexidine digluconate aqueous solution, and sterile surgical drapes will be used. Following these initial steps, one of the surgical sites (as selected) will be infiltrated with either 6 mL of 0.5% racemic bupivacaine + 0.2 mL of epinephrine or 4 mL of 0.75% ropivacaine with 0.2 mL of epinephrine, with approximately 25 mg of anesthetic injected. The surgical procedure will then begin. A Neumann incision with diverticulum will be made on the distal side of the adjacent mandibular second molar, followed by mucoperiosteal detachment, osteotomy, and odontosection (if necessary). The tooth will then be luxated and extracted using levers. The surgical wound will be cleaned and sutured with single or X-shaped stitches using 4-0 polyglactin sutures. Suture removal will take place between 7 and 10 days postoperatively. Before discharge, while

still in the hospital, patients will receive intravenous administration of 2g of dipyrone every 6 hours, 40mg of tenoxicam once daily, 100mg of tramadol every 8 hours, 600mg of clindamycin every 6 hours, and 4mg of ondansetron every 8 hours.

Postoperative instructions and necessary medications will be provided to patients both verbally and in writing, according to the protocol recommended by the hospital (APPENDIX B). Suture removal will be performed in an outpatient setting at the Hospital de Clínicas de Porto Alegre between 7 and 10 days postoperatively.

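### Section 4.8 records net aspirated volume, not site blood loss: it subtracts all water used from the bottle alone and has no term for unaspirated blood, saliva or late first-site ooze

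*Protocol*

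**What the plan says.** Section 4.8 of the protocol fixes the measurement rule. The basis is the suction bottle: "The intraoperative bleeding assessment will be quantitative, based on the blood collected in the collection bottle". The correction is for irrigation: "The amount of distilled water used will be subtracted from the total aspirated volume". The reading is taken when the suture is completed. For the second site the water used, "along with the volume present in the collection bottle prior to the incision at the second site, will be subtracted".

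The Summary gives the window as running "from the time of incision to the final suture, at each surgical site". Section 3.2 makes the result a specific objective: "Measure the amount of intraoperative bleeding (in mL) during procedures performed with 0.5% bupivacaine", and likewise for ropivacaine.

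Two facts in section 4.6 bear on the rule. Both teeth come out in one session: "patients undergo a single surgery for the extraction of the lower right and lower left third molars". Fluid other than blood and irrigation also enters the mouth before incision: "Extra and intraoral antisepsis will be performed using a 0.12% chlorhexidine digluconate aqueous solution". Section 4.8 states a prior bottle volume for the second site but none for the first.

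The protocol describes no gauze weighing, no haemoglobin measurement in the aspirate, no separate bottle per site and no account of water recovered.

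**The concern.** The rule subtracts water that was used, but counts only fluid that was aspirated. The two match only if every mL of water returns to the bottle. Blood that is swallowed, absorbed or left in the mouth is lost to the measure. Saliva and other fluid that is aspirated is counted as blood. During the second procedure the first socket lies in the same mouth, so any ooze from it that is aspirated then is credited to the second drug. Subtracting the earlier bottle volume removes only fluid collected before the second incision, so it does not correct this.

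Haemostasis is one of the three outcomes in the general objective. The recorded value is a difference between aspirated volume and water used, so a modest fluid imbalance could be as large as the blood loss being compared.

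**Working it through.** The protocol states no mean, standard deviation or difference in mL, so there is no bleeding figure to reproduce. The check is a volume balance.

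**Balance.** For one site let B be true blood loss, U blood that does not reach the bottle, W water used, R water not recovered, S saliva or other non-blood fluid aspirated, and O first-site ooze aspirated after the second incision (zero at the first site).

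- Fluid added to the bottle = (B − U) + (W − R) + S + O
- Recorded value = that amount − W = B − U − R + S + O

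The recorded value equals B only if U + R = S + O. Nothing in section 4.8 secures this.

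**Size and sign under assumed volumes** (none is in the protocol):

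- B = 20, U = 10, R = 10, S = 0, O = 0: 20 − 10 − 10 = 0 mL.
- B = 20, U = 0, R = 0, S = 5, O = 3: 20 + 5 + 3 = 28 mL.
- B = 30, U = 6, 200 mL water with 5 to 10% not recovered (R = 10 to 20), S = 5: 30 − 6 − 10 + 5 = 19 mL, down to 30 − 6 − 20 + 5 = 9 mL. That is 11/30 = 37% to 21/30 = 70% too low.
- B = 30, U = 3, 100 mL water with 5% not recovered (R = 5), S = 5: 30 − 3 − 5 + 5 = 27 mL, 10% too low.
- B = 30, U = 0, 200 mL water with 2% not recovered (R = 4), S = 5: 30 − 4 + 5 = 31 mL, 3% too high.

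**Order effect.** O enters the second site only. If one drug is given second in a of the 15 patients, the difference in means shifts by (2a − 15)/15 mL per mL of ooze:

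- a = 8: 1/15 = 0.07
- a = 10: 5/15 = 0.33
- a = 11: 7/15 = 0.47

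The Summary says administration was alternated between patients, which gives 8/7. Section 4.4 says simple randomization. If simple randomization also sets the order, the binomial probability of a 10/5 or more uneven split among 15 is 0.30, and of 11/4 or more uneven 0.12. With assumed ooze of 0.1 to 0.3 mL/min over an assumed 30 minutes (3 to 9 mL), the shift is about 0.2 to 0.6 mL at 8/7 and 1 to 3 mL at 10/5.

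**Noise.** Section 4.1 (sample calculation) takes 15 patients, a 5% level and 80% power from an earlier study, with no effect size. If the test is two-sided (sidedness is not stated), 15 pairs at 80% power imply a standardized paired difference of (1.960 + 0.842)/√15 = 0.72, or 0.78 with the t distribution. Measurement error whose standard deviation is r times that of the true paired differences divides 0.78 by √(1 + r²). Power falls from 80% to 71% at r = 0.5 and to 51% at r = 1. Both ratios are assumed.

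**The case against.** The strongest reply is that the trial is comparative and split-mouth. Saliva, unrecovered water and unaspirated blood arise at both sites under the same rule, so their average largely drops out of the difference between drugs. This stands in part. It does not cover O, which enters one site only. Nor does it cover irrigation that differs between sides: section 4.6 has tooth sectioning only where needed, so water use may be unequal. It also does nothing for the absolute mL in section 3.2.

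A second reply is that the measure is openly disclosed: the Summary calls it the blood volume aspirated into the collection vial. That is fair as to transparency, but the objective presents the result as the amount of bleeding.

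Third, intraoperative gauze is not mentioned; gauze appears only in the home-care instructions of Appendix B. This stands. Loss into gauze is an inference about oral surgery. Unrecovered water, saliva and late ooze do not depend on it.

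A reader might infer that the comparison is tilted against whichever drug goes second. The documents do not support that for the trial as a whole: under alternation the shift is about 0.07 mL per mL of ooze, and it becomes material only if order is left unbalanced.

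**Conclusion.** The point holds as a defect of measurement. The rule in section 4.8 yields net aspirated volume, and the second-site subtraction does not repair it. The consequences are biased absolute mL, extra noise in a comparison of only 15 pairs, and an order effect if drug order is unbalanced, on which the Summary and section 4.4 differ.

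A reader might go further and conclude that bleeding will be understated by some stated fraction, such as 37 to 70%. The documents do not support any such figure. Blood loss, water volume, recovery and saliva are all assumed, and other plausible values give 10% too low or 3% too high. The volume balance itself rests on section 4.8 alone; every mL and power figure above, apart from the 15 pairs, the 5% level and the 80% power, rests on assumptions.

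**What to change.** Amend section 4.8 as follows.

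- Weigh any gauze used at each site dry and again when that site's suture is completed. Add the weight gain, taking 1 g as 1 mL, to the bottle volume before subtracting the water used. This recovers both the blood and the water held in gauze.
- Empty the mouth by suction before each bottle reading, so that less water is subtracted without having been collected.
- Read the bottle just before the first incision as well as the second, so that fluid from antisepsis is not counted at the first site.
- Report the result as estimated blood loss, and note that saliva and late first-site ooze remain uncorrected.
- Report it by site order as well as by drug, and reconcile the Summary with section 4.4 on how order is set.

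The cost is a scale and a few minutes of weighing per site by the existing team. The change reduces the error but does not remove it.

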4.10 DATA ANALYSIS

A descriptive analysis will be performed on the changes in vital signs observed during the operation (if any). A direct comparison and calculation of the averages will be made between the values observed in both the postoperative analgesia evaluation and the transoperative bleeding assessment.

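### Section 4.8 reads both sites' blood loss off one cumulative bottle, which adds avoidable reading noise to the within-patient difference; a fresh bottle per site is a cheap improvement

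*Protocol*

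**What the plan says.** Bleeding is one of the three outcomes in the general objective (Protocol, section 3.1), and it has its own specific objective in section 3.2: "Measure the amount of intraoperative bleeding (in mL) during procedures performed". Both teeth are removed in one operation (section 4.6): "patients undergo a single surgery for the extraction of the lower right and lower left third molars".

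Section 4.8 makes the measurement quantitative, "based on the blood collected in the collection bottle". For the first site, "The amount of distilled water used will be subtracted from the total aspirated volume", and "This value will be recorded at the time the suture is completed". For the second site the level is taken when that site's suture is finished. The water used, "along with the volume present in the collection bottle prior to the incision at the second site, will be subtracted".

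That last subtraction is needed only if the bottle is neither changed nor emptied between sites. The section gives no graduation, weighing, repeat reading or other check on the level. Section 4.10 then plans the contrast: "A direct comparison and calculation of the averages will be made between the values observed".

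**The concern.** The bottle level in the middle of the operation does two jobs. It is the end value for the first site and the starting value for the second. If it is read too high, the first site is credited with blood that is then taken away from the second. The two sites carry different drugs, so the error goes straight into the drug comparison. The total for the two sites does not change, so a check on total blood loss would not show it.

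At stake is the precision of the hemostasis comparison, which rests on only 15 within-patient differences. The sample size was set for convenience (section 4.1, sample calculation), with no SD or target difference for bleeding. The plan therefore shows no margin for absorbing extra measurement noise.

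**Working it through.** The protocol has no figure of its own for reading accuracy or expected blood loss, so there is nothing to reproduce. The check is error propagation on the section 4.8 formulas.

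**Inputs**
- From the Protocol: one bottle, the two subtraction rules (4.8), direct comparison of the two values (4.10), 15 patients (4.1).
- Assumed: equal and independent error SD s for each separate reading; readings to the nearest mark g, so s = g/√12; SD of the within-patient difference without reading error = 20 mL; error in the water volumes ignored.

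**Step 1: the difference.** Let M be the mid-operation level, F the final level, and W1 and W2 the water used.
- First site: B1 = M − W1
- Second site: B2 = F − M − W2
- Difference: D = B1 − B2 = 2M − F − W1 + W2

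An error e in M moves D by 2e. Illustration with assumed true bleeding of 40 mL per site and 100 mL of water at each: e = +10 mL gives 50 and 30 mL, a difference of 20 mL where the truth is 0.

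**Step 2: reading variance of D**
- One mid-operation reading used for both sites: 4s² + s² = 5s²
- Two independent readings (M1 at the first suture, M2 before the second incision), D = M1 + M2 − F − W1 + W2: 3s²
- Empty bottle per site: 2s²

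Against separate bottles the variance ratio is 2.5 or 1.5, and the SD ratio √2.5 = 1.58 or √1.5 = 1.22. A simulation with 1,000,000 draws gave 4.99, 3.00 and 2.00 for the three cases.

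**Step 3: effect on precision.** Half-width of the 95% confidence interval = t(0.975, 14)/√15 × SD = 0.5538 × √(20² + k·s²), with k = 5, 3 or 2. Without reading error it is 0.5538 × 20 = 11.1 mL.

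| Mark g (mL) | s (mL) | One bottle, one mid reading (5s²) | One bottle, two independent readings (3s²) | Separate bottles (2s²) |
|---|---|---|---|---|
| 10 | 2.89 | 11.6 | 11.4 | 11.3 |
| 25 | 7.22 | 14.2 | 13.1 | 12.4 |
| 50 | 14.43 | 21.0 | 17.7 | 15.8 |

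Example, g = 25: 0.5538 × √(400 + 5 × 52.08) = 0.5538 × 25.70 = 14.2 mL.

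**Step 4: noise or bias.** The sign of the error follows site order. If drug A is given first in k of 15 patients, a constant error e shifts the mean drug difference by 2e(2k − 15)/15.
- 8:7 split, as alternation would give: 2e × 1/15 = 0.13e.
- If order instead followed unrestricted simple randomization, the expected absolute imbalance is 0.21 of patients, so the shift is about 0.42e on average. A split of 10:5 or worse has probability 0.30.

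**Step 5: weighing, to the nearest 1 g, taking 1 g as about 1 mL.** s = 1/√12 = 0.29 mL.
- Separate bottles, each weighed before and after: 4s², half-width from weighing alone 0.5538 × √(4 × 0.0833) = 0.3 mL.
- One bottle weighed at four moments, with the same rounding at the two middle ones: 6s², half-width 0.5538 × √(6 × 0.0833) = 0.4 mL. The middle error still counts twice, but it is small.

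**The case against.** The subtraction rule is arithmetically correct and contradicts nothing in the protocol. Three further objections carry weight.

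- **Doubling is not certain.** Section 4.8 names two moments, the end of the first suture and the time before the second incision. These could be two readings. If their errors are independent, each enters once and the variance is 3s². This stands: the protocol says neither that one reading is reused nor that two are made. Identical rounding of an unchanged level, or an offset common to both readings, would still count twice.
- **The size is unknown.** Material harm needs a coarse bottle, and nothing in the documents indicates one. At 10 mL marks, on the assumptions above, separate bottles gain only 0.3 mL of half-width. This also stands. The 50 mL row alone cannot carry the point.
- **The confidence interval is not the protocol's yardstick.** Section 4.10 plans only averages and a direct comparison. True, but the averages carry the same noise whether or not an interval is reported.

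A reader might infer that the shared bottle favors one drug. The documents do not support that. The error follows site order, and the protocol's summary says of the anesthetics that "their administration was alternated between patients", so a constant error nearly cancels. Section 4.4 describes simple randomization, under which cancellation is less assured if order followed it, but no systematic direction toward one drug results.

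**Conclusion.** The point holds as a low-severity one about precision. The one-bottle rule inflates the reading variance of the within-patient difference by a factor of 2.5 if one mid-operation reading serves both sites, or 1.5 if two independent readings are taken. These ratios need only equal reading error. The cost in mL rests on the assumed 20 mL between-side SD and the assumed graduation: negligible at 10 mL marks, modest at 25 mL, and substantial only at 50 mL.

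It would go too far to conclude that a real hemostasis difference will be lost, or that implausible or negative values will occur. Both depend on blood loss relative to graduation, and the protocol gives neither. Error in the water volumes could produce such values even with separate bottles.

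**What to change.** Change section 4.8 to use a new or emptied collection bottle for each surgical site. Preferably weigh it before the incision and after the final suture of that site. The net amount, less the measured water used at that site, is that site's value. If volume is still read by eye, state the graduation.

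If only one bottle can be used, weigh it at each incision and each final suture. This makes the doubled error small but does not remove it. Neither version reduces error in the water volumes, so these should be measured and recorded for each site.

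The cost is about 15 extra bottles (one per patient), a few weighings by staff who already record the volume, and a short edit. Taking 1 g as 1 mL adds an error assumed to be a few percent of the blood mass, common to both drugs. Patient care does not change.

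The protocol's summary is partly in the past tense. If the operations are already done, what remains is to report the bottle's graduation, whether the mid-operation level was read once or twice, and this limitation.

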4.9 EVALUATION OF POSTOPERATIVE ANALGESIA

To assess postoperative analgesia, a VAS will be used, in which patients will rate their pain from zero (no pain) to ten (worst pain ever felt) at different postoperative time points: T0 (immediate postoperative period, as soon as the patient is lucid), T1 (1 hour after T0), T2 (12 hours after T0), T3 (18 hours after T0), and T4 (24 hours after T0). Two scales will be used for each postoperative time point: one for the left side and one for the right side. These values will be recorded, compared, and presented in the results.

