4.7 ASSESSMENT OF VITAL SIGNS DURING THE OPERATIVE PERIOD

Intraoperative vital signs will be assessed by the Anesthesiology and Perioperative Medicine Service of the Hospital de Clínicas de Porto Alegre, always led by the same care team. Heart rate, blood pressure, and oxygen saturation will be measured and recorded before, immediately after, 1 minute after, and 5 minutes after the injection of each anesthetic. Significant changes, such as hypo or hypertension, bradycardia or tachycardia, and hypoxia, will be recorded and presented in the results.

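### Both sides' VAS ratings run on one clock although the sites are treated in sequence, and comparing plain averages leaves any order effect in the computed error, mainly at T0 and T1

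*Protocol*

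**What the plan says.** Section 4.9 sets a single time origin per patient: "T0 (immediate postoperative period, as soon as the patient is lucid), T1 (1 hour after T0"). The later ratings count from the same origin: "T2 (12 hours after T0), T3 (18 hours after T0), and T4 (24 hours after T0"). Two scales are completed at each time, "one for the left side and one for the right side", so both sides are rated at the same clock time.

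The sites are treated in sequence. In section 4.6, "one of the surgical sites (as selected) will be infiltrated with either 6 mL of 0.5% racemic bupivacaine" or with the ropivacaine solution, and surgery then starts. Section 4.7 takes vital signs up to "5 minutes after the injection of each anesthetic", which treats the injections as separate events. Section 4.8 corrects the second site's blood volume for irrigation water, "along with the volume present in the collection bottle prior to the incision at the second site".

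On how order is set, the Summary says: "To minimize systemic interference from the anesthetic agents, their administration was alternated between patients". Section 4.4 instead describes a simple randomization just before surgery. It does not say whether that fixes the side, the order or both.

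The analysis in section 4.10 is: "A direct comparison and calculation of the averages will be made between the values observed in both the postoperative analgesia evaluation" and in the bleeding assessment. It does not mention operating order or time since injection.

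**The concern.** If the second site is injected roughly one operation after the first, then at any given rating the two sides differ in two ways: the drug, and the time since block and wound. The second difference has a sign that depends on which drug went first. Each patient's bupivacaine-minus-ropivacaine difference therefore equals the drug effect plus or minus an order effect.

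Alternating the order makes these signs nearly cancel in the mean over patients. It does not remove them from the spread of the individual differences, and any standard error, interval or paired test is computed from that spread. With 15 pairs precision is already limited, so the analysis should use a factor that the design itself alternates.

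**Working it through.** **1. The plan's own figure.** Section 4.1 takes 15 patients from an earlier split-mouth study, with 5% significance and 80% power. It gives no effect size or SD, so the number cannot be reproduced, only solved backwards. For a two-sided paired comparison (sidedness assumed), the detectable difference is (1.960 + 0.842)/√15 = 0.72 SD of the within-patient difference. With the noncentral t on 14 df it is 0.78 SD, which is used for the power figures below.

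**2. How large the clock offset is.** The protocol gives no operating times. Assume 20 to 60 minutes between the two injections and 45 to 75 minutes from the second injection to lucidity. The offset as a share of time since the first injection is offset/(offset + minutes from second injection to lucidity + minutes after T0):

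| Rating | Smallest | Largest |
|---|---|---|
| T0 | 20/95 = 21% | 60/105 = 57% |
| T1 (1 h) | 20/155 = 13% | 60/165 = 36% |
| T2 (12 h) | 2.5% | 60/825 = 7.3% |
| T3 (18 h) | 1.7% | 5.1% |
| T4 (24 h) | 1.3% | 3.9% |

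The offset is material at T0 and T1 and small afterwards.

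**3. Model.** For patient i, Dᵢ = τ + k·sᵢ + eᵢ. Here s = +1 if bupivacaine went first and −1 if ropivacaine did, and e has SD 1 (the within-order SD of the drug difference). The order effect k is an assumption, taken from 0 to 1.

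**4. Order split 8:7.**
- Mean of s = 1/15, so the bias of the plain mean is k/15: 0.03 SD at k = 0.5 and 0.07 SD at k = 1.
- True standard error of the plain mean = 1/√15 = 0.258 SD, whatever k is.
- Expected sample variance of D = 1 + k²·(15/14)·(1 − 1/225) = 1 + 16k²/15. The computed standard error is therefore inflated by √(1 + 16k²/15).
- Unadjusted 95% half-width = 2.145 × that factor/√15.
- Half-width with an order term = 2.160/√(15 × (1 − 1/225)) = 0.559 SD.

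Power and type I error come from 100,000 simulated trials:

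| k | Inflation of computed SE | Half-width, plain (SD) | Half-width, with order (SD) | Power, plain | Type I error, plain |
|---|---|---|---|---|---|
| 0 | 1.000 | 0.554 | 0.559 | 80% | 4.9% |
| 0.25 | 1.033 | 0.572 | 0.559 | 80% | 4.4% |
| 0.5 | 1.125 | 0.623 | 0.559 | 76% | 3.1% |
| 0.75 | 1.265 | 0.700 | 0.559 | 69% | 1.6% |
| 1 | 1.438 | 0.796 | 0.559 | 58% | 0.7% |

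With order in the model, power stays at 79 to 80% throughout. The two half-widths are equal when 1 + 16k²/15 = (0.559/0.554)², that is, at k of about 0.13.

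**5. Order set by simple randomization.** The chance of an 8:7 split is 39%, and of 10:5 or worse 30%. The true standard error of the plain mean is now √((1 + k²)/15), which is 0.289 SD at k = 0.5 and 0.365 SD at k = 1. Simulated power of the plain comparison is 78%, 71%, 61% and 50% at k = 0.25, 0.5, 0.75 and 1, against about 77% with an order term. With no order effect the term costs more here than under 8:7: simulated standard error 0.2685 against 0.2581 SD (4% larger), and power 77% against 80%.

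**6. Bleeding.** The lucidity clock plays no part. Section 4.8 removes what was in the bottle before the second incision, so each site has its own volume. Subtraction alone creates no order effect.

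**The case against.** Several points against this are fair.

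- **A model term is ordinary SAP content.** A SAP may exist and could add one, and averaging over two order groups is still a calculation of averages. This stands in part. However, section 4.9 fixes the clock, section 4.10 states the comparison, and neither ties order or injection time to the VAS data that a SAP would need.
- **No test or interval is planned in section 4.10.** True, so the loss appears only in the spread of the differences or in a test added later. The general objective in section 3.1 is framed as finding a significant difference, so some such calculation is to be expected.
- **The order effect is assumed.** True. Nothing in the protocol supports k of 0.5 or 1 over 0.25, where the computed standard error grows by only 3% and power is still about 80%.
- **The shared clock is inherent** in treating both sides in one session under general anaesthesia. True; it is not an error in itself, and T0 to T4 can stay.

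A reader might also infer more than the text supports:

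- That the drug comparison is biased, or the estimate itself less precise. With near balance neither holds: the bias is k/15 SD and only the computed error grows, which makes a test conservative.
- That all five ratings are affected alike. The offset is small from 12 hours.
- That bleeding carries an order effect because the second value comes by subtraction. No mechanism is shown.
- That injection times are not kept. Section 4.7 already anchors observations to each injection, and section 4.8 identifies the second site. The protocol simply does not say that clock times are kept or linked to the VAS.

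**Conclusion.** The point holds as an inexpensive improvement to the analysis. The single clock, the sequential sites and the plain averages are all in the protocol. The moment of the second injection is not written out, so the sequence rests on the natural reading of sections 4.6 to 4.8.

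Under near-balanced order, ignoring order makes the computed standard error about 3%, 12.5% and 44% larger at k = 0.25, 0.5 and 1, and adjustment brings no gain below k of about 0.13. If simple randomization sets the order, an uneven split is likely and the true standard error rises as well. The Summary and section 4.4 leave open which case applies. For VAS the weight falls on T0 and T1. For bleeding, an order effect is possible but not demonstrated, so an order term there serves consistency only.

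**What to change.** 1. Reconcile the Summary with section 4.4: state what the randomization decides, and how operating order is set.
2. In section 4.9, carry two items into the VAS data set: which site was operated on first, and the clock time of each site's injection. Section 4.7 already observes each injection. Report hours since injection for each side beside T0 to T4.
3. In section 4.10, analyse the within-patient drug difference at each VAS time with operating order as a two-level term. Equivalently, take the mean difference within each order group and average the two means. Use the same form for bleeding, for consistency.

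The cost is a few entries on the case form and one degree of freedom. With near-even order and no order effect, the interval is about 1% wider (0.559 against 0.554 SD). If order is left to simple randomization, the standard error is about 4% larger when order has no effect. The ratings, assignment and treatment need not change for the analysis term.
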